4.3.2. Clinical examination

A clinical examination of the study participants assessing general health, anthropometric parameters including height and weight as well as frontal temperature using an frontal no-touch thermometer will precede the treatment. Each participant will be asked to provide a finger-prick blood sample for haemoglobin (Hb) levels, which will be detected using a HemoCue analyzer (Hb 301 system, Angelholm, Sweden). To avoid accidental treatment of pregnant women all female participants will be asked to provide a urine sample to be subjected to a pregnancy rapid diagnostic test at baseline. Women will be strongly advised to avoid becoming pregnant during the entire study period. All trial participants will further be asked about existing clinical symptoms before drug administration.

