4.3.3. Adverse effects assessment

Participants will be kept for 3 hours after treatment administration to observe any possible acute adverse events (AEs) and re-assessment will be done at 24 hours post-treatment. Additionally, interviews will be conducted to determine the emergence of clinical symptoms such as headache, abdominal pain, itching, nausea, vomiting and diarrhea directly before treatment within the scope of baseline assessment. At 3 and 24 hours after treatment and retrospectively at days 14-21, 42-49 and 63-70 days post-treatment, participants will again be interviewed for the assessment of adverse events. Symptoms arising within the time span of 14 days after treatment and the respective follow-up time points will be monitored actively by local health workers who will report incidences to the study team. Any symptoms will be recorded in the case report form (CRF) and immediate action will be pursued if indicated.

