4.6. Schedule of visits

Table 1. Schedule of visits

	Screening / Baseline / Treatment / Safety					Follow-up period		
	Day -90	Day -3 - 0	0 h	1-3 h	24 h	Day 14-21	Day 42-49	Day 63-70
Informed consent	X							
Diagnosis (stool exam) ^(a)	X					X	X	X
Baseline data ^(b)	X							
Questionnaire	X							
Medical history ^(c)		X						
Clinical examination ^(d)		X						
Physical examination ^(e)		X						
Randomization administration of treatment			X					
Capturing AEs ^(f)				X	X	X	X	X
Capturing SAE ^(f)				X	X	X	X	X

^(a) based on duplicate Baermann assays of three stool samples. Daily stool sample will take place in 50-100 adults between day 0 and day 28.

^(b) date of birth, age, sex, height, weight, body temperature, pulse rate, blood pressure, Hb measurement, pregnancy test and recording of breastfeeding.

^(c) information gained by asking specific questions concerning chronic disease and concomitant medications.

^(d) investigation for signs of disease: head ache, abdominal pain, nausea, vomiting, diarrhea, itching, other symptoms.

^(e) physical examination on ear, nose, throat, eyes, lungs, lymph nodes and skin.

^(f) a standardized symptom questionnaire is used, that includes the recording of headache, abdominal pain, itching, nausea, vomiting, diarrhea, allergic reaction, others.

5. Selection of the trial participants

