6.1.1. Types of adverse events

The term “adverse event” is defined as:

Any untoward medical occurrence in participants or clinical investigation subject administered a pharmaceutical product and which does not necessarily have to have a causal relationship with this treatment.

An AE can therefore include any of the following events, which develop or increase in severity during the course of the study, after administration of the study product:

- a) Any unfavorable and unintended sign (including an abnormal laboratory finding, for example), symptom, or disease temporally associated with the use of a medicinal product, whether or not considered related to the medicinal product.
- b) Any abnormality detected during physical examination.

These data will be recorded on the appropriate CRF sections, regardless of whether they are thought to be associated with the study or the drug under investigation. “Associated with the drug” means that there is a reasonable possibility that the event may have been caused by the drug.

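### The pre-dose symptom question covers the moment, the later interviews cover weeks, so the before-after adverse event contrast in 8.3 rises at days 14-70 even if the drug does nothing

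*Combined protocol and SAP*

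**What the plan says.** **Before dosing.** Section 4.3.2 states: "All trial participants will further be asked about existing clinical symptoms before drug administration". Section 4.3.3 places the symptom interview "directly before treatment within the scope of baseline assessment". Table 1 (4.6) has a clinical examination on day -3 to 0, described in footnote (d) as "investigation for signs of disease: head ache, abdominal pain, nausea, vomiting, diarrhea, itching, other symptoms". Medical history, footnote (c), is "information gained by asking specific questions concerning chronic disease and concomitant medications". No look-back period for symptoms is given. The only pre-dose look-back of stated length is in 5.6: one month, for medications and their indications.

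**After dosing.** Section 4.3.3: "At 3 and 24 hours after treatment and retrospectively at days 14-21, 42-49 and 63-70 days post-treatment, participants will again be interviewed". For symptoms between visits it adds that they "will be monitored actively by local health workers who will report incidences to the study team". This monitoring has no pre-dose counterpart.

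**What counts.** Section 6.1.1 covers events "which develop or increase in severity during the course of the study, after administration of the study product", recorded whatever the suspected cause. No rule deals with a recurring complaint that happens to be absent at dosing.

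**Analysis.** Section 8.3 evaluates adverse events descriptively as the change in the proportion reporting them from before to after treatment. It does not say which post-dose interview supplies the second proportion. The synopsis (Statistical Analyses) instead describes frequency tables compared between treatment groups.

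**The concern.** The two sides of the 8.3 contrast are measured over different lengths of time. Before dosing, a participant reports a symptom only if it is present then. At the three later visits the same participant reports it if it occurred at any time over several weeks. Someone with a headache every week or two, but none on the dosing day, enters as symptom-free and is later counted as having developed a headache. Headache, abdominal pain, itching, nausea and diarrhoea, all on the prompt list, are the kind of complaint that comes and goes.

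Three features of this trial make it matter:

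- Safety and tolerability of moxidectin is the first secondary objective, and section 3 states it for the 175 moxidectin recipients themselves. Absolute rates in that arm are therefore a target.
- There is no placebo arm (10.6) to show the background.
- The late visits are deliberate. Section 2 plans prolonged safety follow-up because of moxidectin's long half-life, and the mismatch falls on exactly those visits.

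**Working it through.** The documents give no adverse event or background symptom rate, so there is no planned figure to reproduce. The sample-size figures in 8.2 do not enter the argument.

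**Step 1: windows implied by 4.3.3.** Time since the previous interview, counting from the 24 h interview:

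- day 14-21: 14 - 1 = 13 to 21 - 1 = 20 days
- day 42-49: 42 - 21 = 21 to 49 - 14 = 35 days
- day 63-70: 63 - 49 = 14 to 70 - 42 = 28 days

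**Step 2: a model with no drug effect.** Let p be the proportion with a symptom at any moment and D the mean episode length in days; both are assumptions. The onset rate when symptom-free is λ = p / ((1 - p) D). The proportion reporting the symptom over a window of W days is 1 - (1 - p) exp(-λW). The pre-dose proportion is p.

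Example, p = 2% and D = 3: λ = 0.02 / (0.98 × 3) = 0.00680 per day.

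- W = 13: 1 - 0.98 × exp(-0.0884) = 10.3%
- W = 20: 1 - 0.98 × exp(-0.1361) = 14.5%

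In 175 moxidectin recipients that is 3 or 4 people before dosing and about 18 to 25 at the first follow-up, from an inert drug.

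| p (before) | D, days | λ per day | Reporting at day 14-21 (W = 13 to 20) | Spurious rise, points |
|---|---|---|---|---|
| 1% | 7 | 0.00144 | 2.8% to 3.8% | 1.8 to 2.8 |
| 2% | 3 | 0.00680 | 10.3% to 14.5% | 8.3 to 12.5 |
| 5% | 3 | 0.01754 | 24.4% to 33.1% | 19.4 to 28.1 |
| 5% | 1 | 0.05263 | 52.1% to 66.8% | 47.1 to 61.8 |

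The rise runs from about 2 to about 62 points. For p = 2% and D = 3, the day 42-49 visit gives 15.0% to 22.8% and the day 63-70 visit 10.9% to 19.0%. The model gives everyone the same rate and perfect recall; clustering within people or forgetting would lower these figures.

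**Step 3: the early interviews.** With W = 1 day, p = 2% and D = 3 give 2.7% against 2%. The worst row above (p = 5%, D = 1) gives 9.9% against 5%. The mismatch is small beside that of the later visits.

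**Step 4: the randomised comparison.** Background reports arise equally in both blinded arms, so with no drug effect the expected difference is zero. With a real effect the difference shrinks. Take drug-caused rates r of 15% and 5%, 175 per arm, and a background b of 30% (all assumed); the observed rate is 1 - (1 - b)(1 - r).

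- b = 0: difference 10 points; z = 0.10 / √(2 × 0.10 × 0.90 / 175) = 3.12
- b = 30%: 40.5% against 33.5%, 7 points; z = 0.07 / √(2 × 0.37 × 0.63 / 175) = 1.36

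No such test is planned. The figures only show the direction and rough size of the dilution, with the whole effect placed in the recall visits.

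**Step 5: does a matched look-back repair the contrast?** Under the same model the pre-dose proportion over W days equals the post-dose proportion over W days. For p = 2% and D = 3 that is 15.0% before and after with W = 21, or 10.9% with W = 14. The expected change is zero when the drug does nothing.

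**Step 6: would it be better to drop symptoms present in the pre-dose look-back?** Use D = 3, a 21-day window, r = 15% against 5% and 175 per arm. Let q = 1 - exp(-21λ). Without the filter the recorded rate is (1 - p)[1 - (1 - q)(1 - r)]; the filter multiplies it by exp(-21λ). z uses the pooled variance as in step 4.

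- p = 5%: 39.1% against 32.6% (z = 1.28) becomes 27.1% against 22.5% (z = 0.98)
- p = 2%: 25.8% against 17.3% (z = 1.93) becomes 22.4% against 15.0% (z = 1.77)

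With equal rates for everyone, the filter discards drug-caused events along with background. It can help the comparison only if symptoms cluster in particular people.

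**The case against.** The strongest reply is that the trial is randomised and double-blind, and the synopsis compares adverse events between groups. Ivermectin recipients face the same interview schedule and show how many reports it generates. This stands for the between-arm comparison. It does not rescue the before-after difference in 8.3 or the absolute moxidectin rates.

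Second, 6.1.1 deliberately records everything that develops after dosing, related or not, and 6.1.3 then assesses relatedness using medical history and concomitant medication. So a recurrent headache recorded as an adverse event follows the definition and is not an error of recording. That stands too. But calling an event unrelated under 6.1.3 needs a reasonable alternative explanation, and the physician will often lack one without a record of usual symptoms.

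Third, something is collected before dosing: chronic disease, concomitant medication, and a month of medications with indications. These may reveal some treated or chronic complaints, but they are not a symptom history. The case report form is not in the documents, so its exact question wording cannot be checked.

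A reader might also make something of the prompt lists, since the post-dose list in footnote (f) ends "vomiting, diarrhea, allergic reaction, others" and the pre-dose list in footnote (d) does not name allergic reaction. Both lists are open-ended, so this carries no weight.

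**Conclusion.** The point holds for the three later visits, for the before-after contrast in 8.3, and for absolute adverse event rates in the moxidectin arm. Following the plan as written produces an apparent rise at those visits for an inert drug. Its size cannot be taken from the documents: about 2 to 62 percentage points at day 14-21 for a single symptom, over assumed prevalences of 1-5% and episodes of 1-7 days, and less with clustering or imperfect recall.

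A reader might infer more, and the documents do not support it:

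- *That the comparison of moxidectin with ivermectin is biased.* It is diluted; both blinded arms are interviewed in the same way.
- *That late adverse event rates mainly measure the look-back.* That depends wholly on the assumed rates.
- *That all adverse event data are affected.* The 3 h and 24 h interviews are little touched, and a symptom present at dosing is captured then and counts only if it worsens.
- *That no choice of analysis helps.* Limiting the before-after contrast to 3 h and 24 h, or relying on the between-arm comparison, removes most of the problem. What analysis cannot do is supply the missing pre-dose history for the later visits.

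No sample size, alpha or power figure changes.

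**What to change.** - **4.3.2, 4.3.3 and Table 1:** before dosing, ask each symptom item twice, once as of now and once over a fixed look-back. Ask about the same fixed look-back at the three later visits, in addition to recording events over the whole interval. Three weeks is one option, but at a day-14 visit it reaches 21 - 14 = 7 days before dosing. Two weeks would avoid this at all three visits.
- **8.3:** name the time points. Compare the 3 h and 24 h reports with the as-of-now answer, and the later visits with the matched look-back. Make the randomised between-arm comparison, already in the synopsis, the main adverse event summary.
- **6.1.1:** leave the definition and the full counts unchanged. Show counts restricted to symptoms that were absent or milder in the pre-dose look-back only as a supplementary table, since step 6 shows that the restriction can weaken the between-arm comparison.

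The cost is a few more questions at interviews that already take place and a small change to the case report form. The pre-dose recall will carry some error of its own. The change must be in place before the first dose.

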4.3.3. Adverse effects assessment

Participants will be kept for 3 hours after treatment administration to observe any possible acute adverse events (AEs) and re-assessment will be done at 24 hours post-treatment. Additionally, interviews will be conducted to determine the emergence of clinical symptoms such as headache, abdominal pain, itching, nausea, vomiting and diarrhea directly before treatment within the scope of baseline assessment. At 3 and 24 hours after treatment and retrospectively at days 14-21, 42-49 and 63-70 days post-treatment, participants will again be interviewed for the assessment of adverse events. Symptoms arising within the time span of 14 days after treatment and the respective follow-up time points will be monitored actively by local health workers who will report incidences to the study team. Any symptoms will be recorded in the case report form (CRF) and immediate action will be pursued if indicated.

4.3.4. Assessment of efficacy after treatment

The efficacy of the treatment will be determined 14-21 days post-treatment by collecting another three stool samples. Stool samples will be microscopically examined for *S. stercoralis* applying each duplicate Baermann technique as well also for potential co-infection with *A. lumbricoides*, *T. trichiura*, hookworm and *Taenia* ssp. eggs using each duplicate Kato-Katz thick smears on the first two stool samples. The efficacy of the moxidectin and ivermectin will further be assessed 42-49 days after treatment and 63-70 days after treatment by duplicate Baermann technique.

Participants will be considered *S. stercoralis* cured if no larvae have been found in any of the stool samples. Infection is calculated as larvae per gram stool (LPG). LPG will be assessed by calculating the mean of the larvae counts from the corresponding multiple Baermann assays and adjusted to the previously weighted used amount of stool sample. At the end of the study (day 70) all participants remaining positive for *S. stercoralis* will be treated with ivermectin (200

µg/kg), the current standard drug against *S. stercoralis* [9]. Study participants positive for co-infection will be treated with the currently and locally standard treatment option.

4.3.5. Household Questionnaire

A household-based questionnaire will be administered to one member of each participating household to adjust for known influencing factors with regard to re-infection and infection intensity [30, 31] in the subsequent analysis and to identify risk factors for residual infections [44]. The questionnaire will assess information on socioeconomic characteristics (e.g. condition and amenities), access to sanitation and water facilities (e.g. latrine, toilet, shower, water source) as well as hygiene behavior (e.g. defecation, hand washing, water use). The questionnaire is based on the core questions recommended by WHO and UNICEF.

4.3.7 Daily stool sampling

Larval excretion pattern is determined from 50-100 participants. Stool will be collected of these participants every day after treatment administration until day 28.

4.3.8 Genetic Profiling

From all *S. stercoralis* positive participants, the extracted larvae will be stored in 70% Ethanol after examination by Baermann at each analysis time point (baseline, follow-up 1, 2 and 3). Samples will be shipped to the investigating laboratory (La Trobe University) at room temperature.

4.4. Measure to minimize bias

Study participants eligible for treatment will be randomly assigned to one of the two treatment arms using a computer-generated stratified block randomization code. The random allocation sequence with varying random blocks of 4 and 6 will be provided by a statistician not involved in enrolment, treatment, and data collection. Separate sequences will be generated for three levels of baseline infection intensity (light ≤1 LPG, moderate >1-10 LPG and heavy >10 LPG). The codes will be held at the Swiss Tropical and Public Health Institute. A copy of this code will be kept in a sealed envelope by one of the co-investigators and will only be opened in emergency situations, determined by the principal investigator (PI) upon consultation with the co-investigators (co-PI). Allocation concealment will be maintained by masking the randomization sequence from the team member conducting the recruitment. Participants are blinded towards the study drugs (double-blinded).

Masking of the outcome assessor is ascertained in all treatment arms since the laboratory technicians determining the larvae counts and presence of egg for efficacy assessment will

have no knowledge of the participants assignment to treatment arm. The blinding will be maintained throughout the trial until data entry and processing are complete and the data have been verified. Following release of the final data, the randomization codes will be released.

4.5. Study duration and duration of participation

The trial will last a maximum of 26 weeks. The screening for the baseline will start 12 weeks prior to the treatment. Follow-up screening will take place 14-21, 42-49 and 63-70 days post-treatment and last for about one week. Schedules of visits are summarized below (Table 1).

4.6. Schedule of visits

Table 1. Schedule of visits

	Screening / Baseline / Treatment / Safety					Follow-up period		
	Day -90	Day -3 - 0	0 h	1-3 h	24 h	Day 14-21	Day 42-49	Day 63-70
Informed consent	X							
Diagnosis (stool exam) ^(a)	X					X	X	X
Baseline data ^(b)	X							
Questionnaire	X							
Medical history ^(c)		X						
Clinical examination ^(d)		X						
Physical examination ^(e)		X						
Randomization administration of treatment			X					
Capturing AEs ^(f)				X	X	X	X	X
Capturing SAE ^(f)				X	X	X	X	X

^(a) based on duplicate Baermann assays of three stool samples. Daily stool sample will take place in 50-100 adults between day 0 and day 28.

^(b) date of birth, age, sex, height, weight, body temperature, pulse rate, blood pressure, Hb measurement, pregnancy test and recording of breastfeeding.

^(c) information gained by asking specific questions concerning chronic disease and concomitant medications.

^(d) investigation for signs of disease: head ache, abdominal pain, nausea, vomiting, diarrhea, itching, other symptoms.

^(e) physical examination on ear, nose, throat, eyes, lungs, lymph nodes and skin.

^(f) a standardized symptom questionnaire is used, that includes the recording of headache, abdominal pain, itching, nausea, vomiting, diarrhea, allergic reaction, others.

5. Selection of the trial participants

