Moxidectin was evaluated as an extremely safe drug. A single-dose of 36 mg moxidectin in healthy adults was the highest dose tested to date that still represented a well-tolerated dose [13]. The 1 x 8 mg, therefore, selected, as the highest dose in our study will not pose any health risk. Most common side effects include hypotension, itching, headache, abdominal pain, fever, dizziness or diarrhea. Serious or even fatal encephalopathy may occur in patients co-infected with *Loa Loa*. Furthermore, moxidectin is known to worsen onchodermatitis in patients with hyperactive onchodermatitis. Cambodia is not endemic neither for *Loa Loa* nor onchodermatitis and thus these symptomatic advents shall not constitute a risk in our study. Nevertheless, patients with symptoms for onchodermatitis will be excluded from the study. Additionally, although conclusive teratogenic data on moxidectin are missing, decreased fetal survival and increased fetal born with malfunctions is observed in some animals studies. Thus, pregnant patients as well as females planning to become pregnant within the next six months will strictly be excluded. Last, owing to the lipophilic nature of moxidectin, extraction of moxidectin to the breast milk of nursing mothers is very likely and could be demonstrated in lactating cows [15]. The risk of moxidectin in nursing infants is though unknown, thus breastfeeding females will also be excluded in this study.

In a small exploratory study using the veterinary formulation, a single-dose of 8 mg of moxidectin, and a small sample size (127 participants) moxidectin has been found to be efficacious against *S. stercoralis* (cure rates of 93.7%) and well tolerated in participants [16]. The follow-up phase 2a, randomized, placebo-controlled, dose-escalation trial conducted this year in northern Lao PDR evaluated the efficacy and safety of 2 mg to 12 mg of the human formulation of moxidectin in 209 participants. All tested moxidectin doses showed a promising tolerability with no safety concerns. 4-12 mg of moxidectin displayed a good efficacy profile in the treatment against *S. stercoralis* infections in adults (CR of 83.1%-88.3%). Since the 8 mg dose (CR of 87.0%; 95% CI: 79.8-91.9) is used for onchocerciasis and currently evaluated for other helminth infections this dose was recommended to take forward in phase 2b and phase 3 trials.

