6.1. Adverse event definition

Few adverse events have been reported following moxidectin or ivermectin administration in STH-infected individuals. The most common AEs were abdominal cramps, headache, nausea, diarrhea, fever and vertigo [11, 12, 45, 46].

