6.2. Methods of recording and assessing adverse events

The observation time for AE starts when the treatment is initiated. Participants will be kept for observation for at least 3 hours following each morning treatment for any acute AEs. During the reporting period, any unfavorable changes in the participant's condition will be recorded as adverse events, whether reported by the participant or observed by the investigator. In case of any abnormal finding, the local study physician will perform a full clinical examination and findings will be recorded. An emergency kit will be available on site to treat any medical conditions that warrant urgent medical intervention.

In addition, participants will also be interviewed by a health worker about the occurrence of AEs 24 hours after treatment.

For all AEs, sufficient information will be pursued and/or obtained so as to permit i) an adequate determination of the seriousness of the event (i.e. whether the event should be classified as a SAE); ii) an assessment of the causal relationship between the AE and the study treatments

(i.e. whether the event should be classified as an adverse drug reaction); and iii) an assessment of intensity of AEs by the study physician. Intensity of AE will be judged by the study physician, following guidelines by the European Medicine Agency (Note for Guidance on Clinical Safety Data Management).

All SAE, unexpected adverse drug reactions, or SUSARs must be reported as described in Section 6.3.

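### Dizziness/vertigo and fever, which the protocol lists among the most common reactions, are not named items in the symptom questionnaire, so their incidence may be under-ascertained

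*Combined protocol and SAP*

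**What the plan says.** **Reactions the protocol expects.** Section 2 (Background information) says of moxidectin: "Most common side effects include hypotension, itching, headache, abdominal pain, fever, dizziness or diarrhea". Section 6.1, on moxidectin or ivermectin in people with soil-transmitted helminths, says: "The most common AEs were abdominal cramps, headache, nausea, diarrhea, fever and vertigo".

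**What participants are asked.** For adverse events and serious adverse events, Table 1 (section 4.6) marks capture at 1-3 h, 24 h and the three follow-up visits. Footnote (f) describes the instrument: "a standardized symptom questionnaire is used, that includes the recording of headache, abdominal pain, itching, nausea, vomiting, diarrhea, allergic reaction, others". Footnote (d), the examination shortly before treatment, has a similar list without allergic reaction and also ends in an open category. Section 4.3.3 says "interviews will be conducted to determine the emergence of clinical symptoms such as headache, abdominal pain, itching, nausea, vomiting and diarrhea" directly before treatment, with the interview repeated at each later contact.

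**What is measured.** Footnote (b) defines the baseline data: "date of birth, age, sex, height, weight, body temperature, pulse rate, blood pressure, Hb measurement, pregnancy test and recording of breastfeeding". Table 1 places these in the screening column only. Section 4.3.2 adds that "frontal temperature using an frontal no-touch thermometer will precede the treatment". No vital sign is scheduled after dosing.

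**What else is recorded.** Under section 6.2, any unfavourable change in a participant's "condition will be recorded as adverse events, whether reported by the participant or observed by the investigator".

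**How it is analysed.** Section 8.3 evaluates adverse events descriptively, as the change in the proportion reporting them from before to after treatment. The synopsis adds frequency tables compared descriptively between the treatment groups.

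**The concern.** A symptom that every participant is asked about by name and one that a participant must raise unprompted are not counted on the same basis. If both sit in one frequency table, the unprompted one can look rarer simply because nobody asked. Here the symptoms left unprompted include two that the protocol itself expects to be common.

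Safety and tolerability is the first secondary objective, adverse events are a listed secondary endpoint, and section 11.2 plans no data and safety monitoring board. The form therefore carries most of the tolerability conclusion. At stake are the reported absolute frequencies of dizziness/vertigo and fever and the before/after contrast for them. The primary cure-rate comparison is not touched.

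**Working it through.** The plan gives no figure for this point to reproduce. The check sets the two lists of expected reactions against the prompted items and the visit schedule, then works through what incomplete capture would do.

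**1. Match the terms.** Abdominal cramps are counted as abdominal pain, and dizziness and vertigo as one symptom.

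| Reaction | Section 2 | Section 6.1 | Named in footnote (f) | Named in footnote (d) and 4.3.3 |
|---|---|---|---|---|
| Headache | yes | yes | yes | yes |
| Diarrhoea | yes | yes | yes | yes |
| Abdominal pain/cramps | yes | yes | yes | yes |
| Itching | yes | no | yes | yes |
| Nausea | no | yes | yes | yes |
| Fever | yes | yes | **no** | **no** |
| Dizziness/vertigo | yes | yes | **no** | **no** |
| Hypotension | yes | no | **no** | **no** |

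Of the 7 terms in section 2, 3 are not named. Of the 6 in section 6.1, 2 are not named. The lists overlap: together they hold 8 distinct reactions, of which 5 are named and 3 are not. Two of those three, fever and dizziness/vertigo, are symptoms a participant can report when asked. Hypotension without symptoms needs a measurement.

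**2. Check the schedule.** There are five post-dose contacts. Temperature and blood pressure are scheduled at 0 of 5. Temperature is taken before treatment, so fever has a measured baseline but only a reported follow-up. Dizziness/vertigo has neither a prompt nor a measurement at either time.

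**3. Effect on absolute incidence.** Let *p* be the true proportion with the symptom and *s* the share captured without a prompt. Recorded cases among *n* participants are *n* × *p* × *s*. The documents give neither *p* nor *s*, so the values below are assumptions chosen only to show the range. For the moxidectin arm *n* = 175 (section 8.2).

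| Assumed *p* | True cases (175 × *p*) | Recorded, *s* = 75% | *s* = 50% | *s* = 25% |
|---|---|---|---|---|
| 2% | 3.5 | 2.6 | 1.8 | 0.9 |
| 5% | 8.8 | 6.6 | 4.4 | 2.2 |
| 10% | 17.5 | 13.1 | 8.8 | 4.4 |

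With *s* = 100% nothing is lost, and the documents do not rule that out.

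**4. Effect between arms.** Both arms use the same form under blinding. If *s* is the same in both, the observed difference is *s* × (*p* moxidectin − *p* ivermectin). With assumed rates of 10% and 5% and *s* = 50%, the recorded rates are 5% and 2.5%. The difference is 2.5 points instead of 5, and the ratio stays at 2. A difference is shrunk and rests on fewer events, but it is not reversed or created.

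**5. Effect on the before/after comparison.** The observed change is *s*(after) × *p*(after) − *s*(before) × *p*(before). With equal capture it shrinks as in step 4. With unequal capture its direction is open. For an assumed 5% at both times, with 25% captured before and 50% after, the recorded change is 2.5% − 1.25% = +1.25 points although nothing changed. A named question at both times removes most of the reason for *s* to differ.

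**The case against.** The case on the other side is substantial.

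- **The lists are open.** Footnote (f) is worded as including its items and ends in a catch-all. The list in section 4.3.3 is illustrative. The case report form itself is not in the documents, so it may hold more items than the protocol names.
- **There are other routes of capture.** Section 6.2 records any change reported or observed, with a full examination after an abnormal finding. Participants are watched for 3 hours, local health workers monitor symptoms actively, and section 5.6 requires medication to be recorded with its indication, so a treated fever leaves a trace.
- **Fever has some baseline.** Temperature is taken before treatment, and fever as acute illness is a ground for exclusion.
- **Hypotension stands on one list.** Section 2 names it. Section 6.1, which concerns the infected population, does not.

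All of this stands, and it rules out three stronger readings. A reader might infer that the safety endpoint does under-count these reactions. The documents show only a risk, because they give no event rate and no capture share. A reader might infer that a moxidectin-ivermectin difference is distorted. With the same form in two blinded arms, no differential capture is shown, and the adverse-event comparison is descriptive only. A reader might also infer that vital signs after dosing are a cheap omission. Readings at the 3 h and 24 h contacts would be 350 × 2 = 700 sets, in community buildings, and section 6.2 describes the 24 h contact as a health-worker interview. That is an added procedure, and the documents do not show it to be near-free.

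What survives is narrower. An open category and a general recording rule make capture possible, but they do not put the question to everyone. The examination in section 6.2 starts only once something abnormal has been found. Neither answers why two reactions on both of the protocol's own lists are missing from all three prompted lists.

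**Conclusion.** The point holds as a risk of under-ascertainment. Dizziness/vertigo and fever are expected by sections 2 and 6.1 but are not named in footnote (d), footnote (f) or section 4.3.3. Their reported incidence may be low relative to prompted symptoms, and section 8.3 has no prompted baseline for them.

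The size cannot be computed from the documents. The counts in the working are illustrations under assumed rates and capture shares, and the loss is nil if capture is complete. The consequence is mainly for absolute incidence and precision. The conclusion assumes that the form follows the lists printed in the protocol. If the actual form already names both symptoms, only the protocol text needs correcting.

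For hypotension the conclusion is limited to a mismatch: section 2 lists it, while Table 1 has no blood pressure after dosing, so an episode without symptoms would not be found by any scheduled assessment.

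**What to change.** Add dizziness/vertigo and fever as named items in footnote (d), footnote (f) and section 4.3.3. Ask them before treatment and at every post-dose contact, in the same words in both arms. In the adverse-event tables, mark which terms were prompted and which came through the open category.

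The cost is two more lines on the paper and tablet forms, with no new visit or procedure. Reported adverse-event rates will probably rise somewhat, because prompting also elicits mild and unrelated complaints. The prompted baseline helps to separate those from changes after treatment.

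On hypotension, the sponsor should reconcile section 2 with Table 1, or state in the report that asymptomatic hypotension was not assessed. The second option costs one sentence.
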